7.5 DATA SOURCES

This study will be conducted using the HIRD, a large administrative healthcare database maintained by HealthCore for use in health outcomes and pharmacoepidemiologic research. The HIRD includes longitudinal medical and pharmacy claims data from health plan members across the United States (US). Member enrolment, medical care (professional and facility claims), outpatient prescription drug use, outpatient laboratory test result data, and health care utilization may be tracked for health plan members in the database dating back to January 2006, and with diagnoses recorded in International Classification of Disease, Version 10 (ICD-10) since October, 2015. Laboratory result data are additionally available for those tests that have been performed using two large, national reference laboratories (Quest and LabCorp) [R14-4278]. The database has been used for the study of numerous diseases, including studies of COPD [R19-2324; R19-2321; R19-2323; R19-2322; P15-11025; P14-12233]

7.6 BIAS

Several potential biases are inherent to any observational study in the HIRD. In the absence of randomization, confounding by indication could be an issue. Controlling by propensity score should limit this bias, but can control only for measured covariates and may produce estimates that are impacted by residual confounding. This is of particular importance in the case of lifestyle factors that are less critical to insurance billing and thus poorly captured in claims data. Quantitative bias analyses can formally describe the extent to which these issues are present, but bias analysis parameters are informed by literature and clinical expert opinion. As such, the accuracy of bias corrected analyses is limited by the accuracy of the assumptions that inform them [R19-3031].

Second, there is the possibility of information bias due to misclassification of the outcomes or exposure or missing data, especially, differential missingness of some data (e.g. eosinophils, which may only be measured in sicker patients). The prescriptions dispensed by a pharmacy but not taken by patients could lead to misclassification of exposure. Pharmacy dispensing data does bring us one step closer to patient use than physician prescribing given that the patient has taken the effort to obtain the medication as instructed, however, information such as indication can only be inferred based on diagnostic patterns.

Proprietary confidential information © 2019 Boehringer Ingelheim International GmbH or one or more of its affiliated companies

7.7 STUDY SIZE

	Tio	+Olo	ICS/LABA	A/LAMA
	Ν	%	Ν	%
New users	8,233	100.0	82,534	100.0
At least 12 months of				
pre-index eligibility	6,263	76.1	50,153	60.8
Age 40 +	6,126	97.8	48,267	96.2
At least 1 diagnosis of COPD	5,469	89.3	42,227	87.5
At least 1 eosinophil % result				
prior to the index date	2,207	40.4	15,699	37.2
Eosinophil result (N, % of				
those with a result)				
0-2%	1,059	48.0	7,488	47.7
2-4%	745	33.8	5,136	32.7
4%+	403	18.3	3,075	19.6
Eosinophil result, patients				
with low exacerbation				
history(0 inpatient and 0-1				
outpatient events at baseline,				
N, %)				
<300 cells/uL	1,381	30.0	9,516	27.3
\geq 300 cells/uL	481	10.5	3,481	10.0
Unknown	2,739	59.5	21,813	62.7
Eosinophil result, patients				
with high exacerbation history				
(1 + inpatient or 2 + outpatien)				
t events at baseline, N, %)			vents	
<300 cells/uL	226	26.0	1,888	25.5
≥300 cells/uL	105	12.1	707	9.5
Unknown	537	61.9	4,822	65.0

Preliminary patient counts in the HIRD are shown here:

In a recent analysis of the risk of exacerbations based on Clinical Practice Research Datalink (CPRD), a total of 2,000 patients per cohort detected a 15% difference in risk of a first exacerbation (hazard ratio 0.85) with over 90% power. As such, overall analyses and analyses that are stratified based on the presence of claims-based indicators of exacerbation are expected to have adequate power. Analyses limited to individuals with specific eosinophils will be more limited. Given low expected sample size, stratification by eosinophil analysis within individuals with exacerbations at baseline will not be performed by Eosinophil categories.

7.8 **DATA MANAGEMENT**

All statistical analysis for the study will be conducted using SAS version 9.4 or higher (SAS Institute, Cary, NC). All sensitive data pertaining to the study will be stored on secured servers with access only permitted by approved study team members.

A number of Information Security policies are enforced, audited, and in place at HealthCore, including complex password requirements and encryption systems. Security mechanisms and policies are in place HealthCore's facilities are standard corporate office space. Office space is segregated and managed by monitored electronic access. HealthCore areas which contain project and study-related documents are only access by HealthCore associates or contract personnel. All non-HealthCore associates must be accompanied by an associate at all times in order to enter these areas. All study related files are kept in locked cabinets and work areas. There are no visible labels or client listings viewable by any visitor or passerby. All passwords and user authentication mechanisms are forced changed at regular intervals and there is automatic locking of workstations after a short period of time (< 15 minutes).

Data Center space is permitted on an as required basis and monitored by electronic access. HealthCore maintains a cumulative record that indicates, for any point in time, the names of authorized personnel, their titles, and a description of their access privileges to the Data Center. Data access is restricted, monitored, logged, and audited. HealthCore's computer networks have been designed to separate patient or physician identified data from de-identified or masked data. Network security, firewalls, and password permissions control which HealthCore personnel have access to patient or physician identifiers. Unless the study protocol calls for patient or physician authorization or a waiver of authorization as granted by an IRB, no research analyst will have access to patient or physician identifiers within HealthCore's computer systems. All research analysis databases have been de-identified. HealthCore's Data Center is also physically secured by a controlled access facility, with only authorized personnel having access to network servers, tape libraries and other media that contains patient identifiers.

Research analysis files used by HealthCore do not contain patient or physician identifiers unless necessary to perform such research; if such is the case, access will be made after receipt of the patient's or physician's authorization or IRB waiver of such authorization has been granted. It is also HealthCore policy to provide for secure storage of study materials, including data, reports, and other files after the study is completed, with a destroy date assigned based on study requirements. HealthCore reviews data requirements for each study to assure that only the minimum of patient or physician information is obtained to answer the research question(s). For those studies where direct patient identifiers are needed for additional data collection such as medical chart abstracts, access to information will be limited to the greatest possible extent within the research team. Both structural and contractual safeguards reinforce policies to minimize the risk of breaching patient or physician privacy. The structural safeguards include a clearly defined data flow process. This process minimizes the risk of individual identifiers being improperly used or disclosed. The contractual safeguards include contractual binding to confidentiality of individuals involved in the research.

Proprietary confidential information © 2019 Boehringer Ingelheim International GmbH or one or more of its affiliated companies

7.9 DATA ANALYSIS

7.9.1 Main analysis

All analyses will be presented for each group (Tio+Olo vs LABA/LAMA/ICS) overall and stratified as follows:

- History of exacerbation: 0 inpatient and 0-1 outpatient events
- History of exacerbation: 1 + inpatient or 2 + outpatient events
- Circulating eosinophils: B-Eos < 300 ug/mL
- Circulating eosinophils: B-Eos 300 ug/mL+
- History of exacerbation: 0 inpatient and 0-1 outpatient events & circulating eosinophils: B-Eos < 300 ug/mL
- History of exacerbation: 0 inpatient and 0-1 outpatient events & circulating eosinophils: B-Eos 300 ug/mL +

We will first describe formation of the study cohort. Patient characteristics at baseline in patients treated with Tio+Olo and patients treated with LABA/LAMA/ICS will be described using standard descriptive statistics. Because eosinophil levels may vary based on exacerbation, we will also provide a count and percentage of the number of individuals whose eosinophil results were recorded within 30 days of an exacerbation event.

High-dimensional propensity scores including both pre-specified and data-derived variables will then be calculated. We will use fine stratification and reweighting of the exposure propensity score to control for measured covariates [R19-3030]. Balance of patient characteristics between the cohorts will be described before and after propensity score application and compared using standardized differences (in the crude population and the reweighted pseudo-population). Standardized differences greater than 0.10 (10%) will be taken to indicate imbalance and further refinement approaches will be applied.

For the analysis of the primary objective, a Cox proportional hazard regression model will be used to perform an as-treated analysis that assesses the effect of current use of LABA-LAMA-ICS combination versus the Tio+Olo combination on the risk of a first COPD exacerbation. It will provide an estimate of the hazard ratio (HR) of a COPD exacerbation associated with LABA-LAMA-ICS use relative to Tio+Olo use, along with 95% confidence intervals (CI).Current use will be defined based on the days supply during the period of overlap, allowing a grace period of 15 days following the end of days supply to account for intermittent use. This approach allows consideration of exposure as time-dependent, accounting for the changes in exposure during the follow-up. In particular, this analysis excludes patients stopping one or more of the drugs prior to the index date.

Stratified analyses will use the same approach. Because not all individuals will have available laboratory result data available, fine stratification and reweighting by propensity score will be repeated within the subset of the cohort with available results to create weighted populations suitable for these stratified analyses. Potential effect-modification by B-Eosinophils and/or exacerbation history will be studied by comparing models with and without interaction terms and through qualitative consideration of differences in stratum-specific estimates.

The analysis of the risk of pneumonia will also use a time-dependent Cox proportional hazard regression model with an as-treated approach, similar to that of the primary analysis.

In addition, we will repeat the primary effectiveness analysis on the time to exacerbation separately for moderate and severe exacerbations.

In terms of healthcare utilization, we will present continuous and categorical variables using standard descriptive statistics to describe total visits and total costs related to inpatient, outpatient, office visit, and emergency care as well as total pharmacy dispensings, distinct medications used, and pharmacy costs. Utilization and costs will be stratified to facilitate comparison between Tio+Olo and LABA/ICS, and presented by individual setting and as a composite. All-cause and COPD-specific data will be shown.

Proprietary confidential information © 2019 Boehringer Ingelheim International GmbH or one or more of its affiliated companies

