7.4.3 Covariates

Patient characteristics at baseline will be assessed for Tio+Olo and LABA/LAMA/ICS user overall and stratified by history of exacerbation, circulating eosinophils, subgroups defined by both exacerbation and eosinophil levels.

We will identify and describe the following demographic characteristics as of the index date:

- Sex
- Age (years, as both a categorical and a continuous variable)
- Calendar year of cohort entry

Proprietary confidential information © 2019 Boehringer Ingelheim International GmbH or one or more of its affiliated companies

- Season of index date (winter, spring, summer, fall)
- US census region of residence
- Insurance type (e.g., Commercial, Medicare)

Additional characteristics will be defined during the 12-month pre-index baseline period:

- Number of previous COPD treatments
- Specific previous COPD treatments
 - LAMA monotherapy
 - LABA monotherapy
 - ICS monotherapy
 - LAMA/ICS combination therapy
 - LABA/ICS combination therapy
- Previous acute COPD exacerbation (measured both overall and in the 30 days prior to cohort entry), categorized as 0, 1, or 2+.
 - All exacerbations (Moderate+Severe)
 - ED visits or dispensings of inhaled corticosteroids/antibiotics (Moderate)
 - Hospitalizations (Severe)
- Use of other respiratory drugs in the 12-month pre-index period:
 - Short-acting beta-agonists
 - Anticholinergics
 - Methylxanthines
 - Muscarinic antagonists
 - Short-acting muscarinic antagonists
- Use of antibiotics for a respiratory condition (e.g., azithromycin)

Chronic comorbidities will be defined using diagnoses identified during all available data prior to the index date, and will include:

- Cardiovascular disease
- Charlson comorbidity index
- Diabetes
- Thyroid disease
- Renal failure
- Autoimmune disease
- Pneumonia
- Obesity*
- Alcohol use disorder*
- Tobacco use or cessation counselling*
- Cancer (excluding basal cell carcinoma)
- * We anticipate limited capture of lifestyle variables known to be risk factors and potential confounders, including obesity, smoking status and excessive alcohol consumption. Although we will describe them as identified in the HIRD, bias analyses to examine the extent to which residual confounding may impact results are also planned.

Additionally to the covariates defined above, we will use the high-dimensional approach to identify variables entering a time-conditional propensity score.

Boehringer Ingelheim	

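### The pre-specified 12-month exacerbation covariates are capped at 2+, so among high-history patients without a COPD admission they cannot separate exacerbation frequencies or show an imbalance in them

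*Combined protocol and SAP*

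**What the plan says.** Section 7.4.3 lists the baseline item as "Previous acute COPD exacerbation (measured both overall and in the 30 days prior to cohort entry), categorized as 0, 1, or 2", the top category being two or more. It is split into all, moderate and severe events. The moderate line reads "ED visits or dispensings of inhaled corticosteroids/antibiotics (Moderate", and the severe line is hospitalizations. No count or category above 2+ is pre-specified.

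Section 7.9.1 lists the stratum "History of exacerbation: 1 + inpatient or 2 + outpatient events" and says that stratified analyses follow the main approach. Re-estimation of the propensity score is stated only for the subset with laboratory results, not for the exacerbation strata.

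The score is not confined to the exacerbation items. Section 7.4.3 says "Additionally to the covariates defined above, we will use the high-dimensional approach to identify variables entering a time-conditional propensity score", and 7.9.1 confirms "High-dimensional propensity scores including both pre-specified and data-derived variables will then be calculated". The named covariates also include "Number of previous COPD treatments", other respiratory drugs and respiratory antibiotics. Neither section says which data feed the data-derived variables or how they are selected.

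The balance rule in 7.9.1 is "Standardized differences greater than 0.10 (10%) will be taken to indicate imbalance and further refinement approaches will be applied".

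**The concern.** Past exacerbation frequency is the protocol's own marker of exacerbation risk, and prescribers are likely to act on it when they choose triple therapy. The covariate stops resolving frequency exactly where patients without an admission enter the high-history stratum. In that subgroup the 12-month items carry no information on frequency, and a balance table built on them shows zero difference whatever the true counts are.

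The planned hazard ratio is triple therapy relative to Tio+Olo. If triple starters in the stratum had exacerbated more often, the leftover difference would push that ratio upward, in favour of Tio+Olo. The abstract names patients at high exacerbation risk with raised eosinophils among the likely ICS responders. Sections 7.4.3 and 7.7 rule out splitting the high-history group by eosinophils, so one stratum estimate carries the high-risk result. Section 7.9.1 also reads effect modification partly from a comparison of stratum estimates.

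**Working it through.** **Possible covariate patterns.** I wrote out every (all, moderate, severe) pattern that the 0/1/2+ coding allows in the high-history stratum, taking the moderate event and the stratum's outpatient event as the same.

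- No admission, 12-month items: one pattern only (2+, 2+, 0).
- No admission, with the 30-day item added: three patterns (0, 1 or 2+ events in the last 30 days).
- At least one admission, 12-month items: six patterns. These items still vary here.

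The constancy is therefore confined to the 12-month items in non-admitted members. The documents do not give the share of the stratum without an admission.

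**Stratum size, from the section 7.7 table.**

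- Tio+Olo: 226 + 105 + 537 = 868; 868/5,469 = 15.9%.
- Triple: 1,888 + 707 + 4,822 = 7,417; 7,417/42,227 = 17.6%.
- Adding the low-history counts (4,601 and 34,810) returns 5,469 and 42,227, so the table is internally consistent.

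**Possible size of bias.** The protocol gives no figure for this, so the model below is an assumption. Let each arm's 12-month count be gamma-Poisson with mean m and dispersion k (the same k in both arms), and treat every stratum member as qualifying through 2+ outpatient events. Assume also that a patient's underlying rate carries over into follow-up.

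1. With q = k/(k+m), P(count ≥ 2) = 1 − q^k × [1 + k(1−q)]. Solve for m so that this equals 0.159 (Tio+Olo) and 0.176 (triple).
2. Given a count x, the expected rate is (k+x)/(1+k/m). Averaged over the stratum it is (k+M)/(1+k/m), where M is the mean count given 2+.
3. The ratio of stratum rates is [(k+M₁)/(k+M₀)] × [(1+k/m₀)/(1+k/m₁)], with 1 = triple and 0 = Tio+Olo. The second factor remains even after conditioning on the exact count. The first is the part that using the count would remove.
4. The standardized difference (SMD) in the true count is (M₁−M₀) divided by the root of the average of the two variances within the stratum.

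| k | m₀ | m₁ | m₁/m₀ | M₀ | M₁ | SMD | Removable factor |
|---|---|---|---|---|---|---|---|
| 0.5 | 0.668 | 0.741 | 1.11 | 3.03 | 3.14 | 0.067 | 1.030 |
| 1 | 0.662 | 0.721 | 1.09 | 2.66 | 2.72 | 0.055 | 1.016 |
| 2 | 0.674 | 0.728 | 1.08 | 2.47 | 2.51 | 0.047 | 1.009 |

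For k = 1 the last column is (1 + 2.721)/(1 + 2.662) = 1.016.

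**Cross-check with a simpler model.** Let the count be 2 + Poisson and let the outcome rate be multiplied by g per extra event. The factor is exp[(g−1) × d], where d is the between-arm difference in mean count. For d = 0.1 and g from 1.1 to 1.3 it is 1.01-1.03, in line with the table, where M₁−M₀ is about 0.04 to 0.11. A factor near 1.10 would need d of about 0.5 at g = 1.2: exp(0.2 × 0.5) = 1.105.

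**The case against.** The strongest reply is that the score contains more than the capped items. The 30-day item still varies in this subgroup. Number of prior treatments, short-acting drugs and respiratory antibiotics are listed. Data-derived variables could pick up repeated ED visits, steroid dispensings or antibiotic dispensings, each of which is codable on its own. This stands. A reader might infer from the cap that exacerbation frequency cannot be adjusted for at all, or that every patient in the subgroup looks identical to the score. The documents do not support either reading. They also do not guarantee adjustment: a 30-day window does not measure annual frequency, and the data-derived candidates and selection rule are not given.

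The second reply is that the effect is small. This also stands. Under the calibrated model the true-count SMD is below 0.10, so even a check on the count might not trigger refinement. A reader might assume a larger gap, for example a triple mean rate 1.5 times that of Tio+Olo, which gives 6-14% on the hazard ratio and an SMD of about 0.27. With a common k that assumption implies 23.1-26.3% of triple users at 2+, against 17.6% in section 7.7, so it conflicts with the protocol's own table and should not be used.

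Third, the constant pattern depends on matching definitions. Section 7.4.2.1 uses an ED visit and/or an antibiotic with an oral corticosteroid on the same day; the covariate in 7.4.3 refers to inhaled corticosteroids/antibiotics. On a literal reading these are different events. This is a condition on the point, and the two passages must be reconciled in any case.

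Finally, 0/1/2+ follows the risk cut-off in section 6. That justifies the stratum boundary, but it gives no reason to stop the adjustment variable at the same place.

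**Conclusion.** The point holds in a limited form. Provided that the moderate covariate and the stratum's outpatient event are the same event, the 12-month exacerbation items are constant among non-admitted members of the high-history stratum. There they neither adjust for frequency nor let the 0.10 rule detect a difference in it. Adjustment is left to the 30-day item, proxies and data-derived variables that the protocol does not specify.

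The calibrated size is about 1-3% on the stratum hazard ratio. It rests on the gamma-Poisson form, a dispersion of 0.5 to 2 common to both arms, all members entering through outpatient events, and no credit for the other variables. The section 7.7 shares mix inpatient and outpatient entry, so they do not fix the outpatient frequency; the bias would be larger only if the arms differed in dispersion or event mix. Nothing here shows that the overall primary hazard ratio is affected. This is a modest gain in confounding control and a more informative diagnostic at almost no cost, not a flaw that invalidates the stratum result.

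**What to change.** - **Section 7.4.3:** enter the 12-month moderate and severe exacerbations in the propensity score as finer counts, for example 0, 1, 2, 3, 4+ or log(1 + count). Keep 0/1/2+ for the descriptive table.
- **Section 7.9.1:** report balance on the mean count within the high-history stratum, before and after weighting, and apply the 0.10 rule to it.
- **Sections 7.4.2.1 and 7.4.3:** reconcile the two descriptions of a moderate exacerbation, so that the covariate, the stratum and the outcome refer to a stated event.

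The cost is wording and a few lines of programming. The events must be counted to assign the 0/1/2+ categories, so no new data are needed.

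### Effect modification should be tested with a robust Wald test and an interval for the ratio of stratum hazard ratios: a likelihood comparison of reweighted Cox models does not hold its level, and the unstated weights decide the direction of the error.

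*Combined protocol and SAP*

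**What the plan says.** All statements are in Section 7.9.1 unless noted.

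- Confounding: "We will use fine stratification and reweighting of the exposure propensity score to control for measured covariates". Balance is then compared "in the crude population and the reweighted pseudo-population", so the analysis population is a weighted one.
- Outcome model: "a Cox proportional hazard regression model will be used to perform an as-treated analysis", giving a hazard ratio with a 95% confidence interval. Exposure is treated as time-dependent.
- Strata: "Stratified analyses will use the same approach". For the eosinophil strata the score and weights are derived again in the patients with laboratory results, "to create weighted populations suitable for these stratified analyses".
- Effect modification by eosinophils or exacerbation history: "comparing models with and without interaction terms and through qualitative consideration of differences in stratum-specific estimates".

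The available text does not say which population the weights target, how they are scaled, how many strata are used, or which statistic and level serve to compare the models. It names no variance estimator. The contents list an Annex 3.4 on statistical considerations, whose text was not available.

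**The concern.** When models with and without an interaction term are compared, the usual statistic is twice the difference in log likelihood, referred to a chi-square distribution. That reference distribution needs a true likelihood. With propensity weights each patient's contribution is multiplied by a weight, so the difference depends on the scale of the weights: doubling every weight doubles the statistic without adding a patient. Normalising the weights removes this scale problem but not the second one, that unequal weights carry less information than the same number of equally weighted patients. Model-based standard errors have both defects.

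Whether the treatment contrast differs by eosinophils or exacerbation history is a stated interest of the study, whose intended readers are payers and prescribers (Section 5). An interaction could be declared where there is none, or a real one missed, because of a scaling choice. The same variance question reaches the overall hazard ratios for exacerbation and pneumonia.

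**Working it through.** **Plan's own figure.** The plan gives no figure for the interaction. Its only power figure (Section 7.7) is over 90% for a hazard ratio of 0.85 with 2,000 per cohort. By Schoenfeld's formula, two-sided 5%, this needs 4 × (1.960 + 1.282)² / (ln 0.85)² = 1,592 events, or 39.8% of 4,000. No event proportion or test level is given, so the figure can be neither confirmed nor carried over to an interaction.

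**Inputs from the table in Section 7.7.**
- Tio+Olo with a result: 1,381 + 481 + 226 + 105 = 2,193.
- Triple therapy with a result: 9,516 + 3,481 + 1,888 + 707 = 15,592.
- At or above 300 cells/µL: (481 + 105) / 2,193 = 26.7% and (3,481 + 707) / 15,592 = 26.9%.
- Total: 17,785.

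**Hand check of the scale effect.** Take equal weights within each arm and equal event proportions. The variance of a log hazard ratio is then proportional to 1/n₁ + 1/n₀. Because the eosinophil split is nearly the same in both arms, the same factor applies to the interaction.
- Real patients: 1/2,193 + 1/15,592 = 0.000520.
- Full-scale whole-cohort weights make each arm count as 17,785: 2/17,785 = 0.000112. True SE over model-based SE = √(0.000520/0.000112) ≈ 2.15. A nominal 5% test rejects 2Φ(−1.96/2.15) ≈ 36%.
- Unnormalised weights to the treated make triple therapy count as 2,193: 2/2,193 = 0.000912. SE ratio = √(0.000520/0.000912) ≈ 0.755. Rejection 2Φ(−1.96/0.755) ≈ 0.9%.

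So opposite errors follow from the arm sizes alone. Unequal weights come on top of this.

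**Simulation.** Weighted Cox models were fitted to 2,193 versus 15,592 patients, 27% with high eosinophils and no true interaction. There were three sets of runs:
- A: 18% with an event, 50 strata, SD of the score's linear predictor 0.6 and 1.0, 400 runs per setting.
- B: about 23% with an event, 50 strata, score c-statistic 0.60, 0.70 and 0.78, 300 runs each.
- C: one score strength, 150 runs.

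With n₁ₛ, n₀ₛ and nₛ the Tio+Olo, triple-therapy and total counts in stratum s, the weights (Tio+Olo; triple) in set B were:
- to the treated, unnormalised: 1; n₁ₛ/n₀ₛ
- to the treated, normalised: 1; (n₁ₛ/n₁)/(n₀ₛ/n₀)
- whole cohort, normalised: (nₛ/n)/(n₁ₛ/n₁); (nₛ/n)/(n₀ₛ/n₀)
- whole cohort, full scale: nₛ/n₁ₛ; nₛ/n₀ₛ

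Rejection of a true null at nominal 5%:

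| Weights | A | B | C | Range |
|---|---|---|---|---|
| Treated, unnormalised | not run | 0.3-3% | 1% | 0.3-3% |
| Treated, normalised | 5.5-6.5% | 6-12% | 4% | 4-12% |
| Whole cohort, normalised | 9-20% | 7-18% | 7% | 7-20% |
| Whole cohort, full scale | 44-58% | 39-50% | 38% | 38-58% |
| Robust Wald, any weights | 4-6% | 5-7% | 4% | 4-7% |

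One simulation standard error in set B is √(0.05 × 0.95/300) = 1.3 points at 5% and √(0.5 × 0.5/300) = 2.9 points at 50%.

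**SE of the log ratio of hazard ratios, set B, c-statistic 0.70.** Model-based versus robust, rows as above:
- 0.1196 versus 0.0955 (robust/model-based 0.80)
- 0.0903 versus 0.0956 (1.06)
- 0.1010 versus 0.1142 (1.13)
- 0.0469 versus 0.1141 (2.43)

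**Overall hazard ratio, set B.** Coverage of model-based 95% intervals was 98-99%, 93-95%, 81-93% and 48-60% in the same order. Robust intervals covered 94-96%.

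**The case against.** Several points on the other side are sound.

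- A reader might infer that the plan omits a robust variance. That cannot be asserted: Annex 3.4 is listed in the contents and could contain one. The ENCePP checklist refers to pages 25-27 for statistical techniques and effect modification, which suggests that Section 7.9 is the operative text but does not prove it.
- The plan names no likelihood-ratio test, p-value or level. A robust Wald test of the interaction term would also fit its words. The likelihood comparison is the natural reading, not the only one.
- A reader might infer that the qualitative look at strata comes without any measure of uncertainty. It does not: each stratum hazard ratio has a 95% interval under the common approach, and the qualitative look is joined to the model comparison, not offered in its place. What is missing is an interval for the ratio.
- The primary objective is the overall comparison. The abstract speaks of exploring variation, and Section 6 labels the combined history and eosinophil analysis exploratory. No objective is a formal test of heterogeneity.
- It is tempting to conclude that false positives approach one in two. That needs full-scale whole-cohort weights, which the documents do not state. With weights to the treated the error is small to moderate if they are normalised, and conservative if they are not.

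These points limit the claim. They do not supply a valid method: the available text leaves open a comparison whose level ranges from well below to far above 5%.

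**Conclusion.** The point holds for the way effect modification is judged. If the models are compared by likelihood, the nominal 5% test can reject anywhere from about 0.3% to 58% of true nulls, depending on weights that the available text does not define. A robust Wald test stays at about 4-7% whichever weights are used, within or close to simulation error of 5%.

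The arm sizes and eosinophil split come from Section 7.7. The event proportion, score strength, number of strata and weight definitions are assumptions, and set B used a single confounder. The runs cover the laboratory subset, not the exacerbation-history interaction in the full cohort. The figures show scale and direction and do not predict this study's error rate. For the overall and stratum intervals the conclusion is conditional: they have the same problem unless Annex 3.4 sets a robust variance.

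**What to change.** In Section 7.9.1:

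1. State the population that the weights target, the weight formula, the scaling and any truncation, for the full cohort and for the laboratory subset.
2. Replace the comparison of models by a robust (sandwich) Wald test of each interaction term in a single weighted Cox model, at a stated level. Aggregate the variance by patient, since time-dependent exposure can give a patient more than one record.
3. Report the ratio of stratum hazard ratios with its robust 95% interval. The qualitative reading of the strata can stay beside it.
4. Use the same robust variance for every weighted hazard ratio, including the primary and pneumonia analyses. If Annex 3.4 already sets this, a cross-reference is enough and only items 1 to 3 remain to be settled.

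The cost is a few sentences and one software option, with no new data. Intervals may widen or narrow depending on the weights. In the c-statistic 0.70 runs the interaction interval on the log scale became 0.80 times as wide with unnormalised weights to the treated and 2.43 times as wide with full-scale whole-cohort weights.
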